Recently, there has been increasing concern among international agencies and national governments over the loss of human potential in children growing up with poverty and malnutrition and possible ways of improving the situation are being explored. Bangladesh Integrated Nutrition Program (BINP) is a major governmental effort to improve malnourished children's nutritional status. This program should reduce mortality and morbidity in children but it is unlikely to also improve their general cognitive, social and emotional development. This proposal concerns incorporating a low cost, feasible, and culturally appropriate program of child development activities into BINP feeding centers with the aim of improving the social and cognitive development of malnourished children and the child rearing skills of their mothers. It is a randomized controlled trial involving the BINP feeding centers, where a group of malnourished children and their mothers will participate in an intervention on child development activities and will be compared with a control group of malnourished children attending other feeding centers. They will also be compared with a group of wellnourished children living in the intervention areas and matched for age, sex, maternal education, and standard of housing. Intervention will include teaching mothers how to play with their children in a way to promote good development, and how to make toys from waste materials. Attention will also be paid to improving maternal child verbal interaction and to improving mothers' self esteem. The intervention program will last for one year. Stimulation at home and the socio-economic status of the family will be measured during a home visit. Before and after the study, the children's developmental levels, behavior, temperament and anthropometry and the mothers' knowledge of child development and child rearing practices will be assessed.

KEY PERSONNEL (List names of all investigators including PI and their respective specialties)

Name	Professional Discipline/ Specialty	Role in the Project
1. [name] [name]	SMO./Paediatrics	Principal Investigator
2. [name] [name]	Associate Professor/Nutrition	Co-PI
3. [name]	Associate Scientist/Nutrition	Co-Investigator
4. [name]	Interim Director/Gastroenterology	Co-Investigator
5. [name]	Professor/Child Development	Co-Investigator

## DESCRIPTION OF THE RESEARCH PROJECT

### Hypothesis to be tested:

---

Concisely list in order, in the space provided, the hypothesis to be tested and the Specific Aims of the proposed study. Provide the scientific basis of the hypothesis, critically examining the observations leading to the formulation of the hypothesis.

---

Mental development of the malnourished children can be improved through psychosocial stimulation added to nutritional supplementation in the BINP community nutrition centers. The child rearing practices of their mothers can also be improved through such a program.

### Specific Aims:

---

Describe the specific aims of the proposed study. State the specific parameters, biological functions/ rates/ processes that will be assessed by specific methods (TYPE WITHIN LIMITS).

---

To establish and evaluate a child development program in BINP nutrition centers to improve the development of moderately and severely malnourished children and their mothers' child rearing practices. The long-term aim is to spread the program to all centers. An additional aim is to determine the deficit in children's development and behavior attributed to protein energy malnutrition.

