In recent years, there has been a marked decline in infant mortality rates in nearly all developing countries. In Bangladesh, rates have fallen from 151 per 1,000 in 1960 to 83 in 1996. Although increasing numbers of children are surviving, the quality of many children's lives remains extremely poor. An enormous number of children under five years are malnourished, as many as 56% are moderately or severely underweight and 18% are moderately or severely wastedi. Many studies have shown that malnutrition of this degree is highly likely to detrimentally affect children's cognitive, motor and social developmentii. They are likely to fail in school and subsequently have poor employment opportunities. Compared with better-educated parents, poorly educated parents tend to have larger numbers of childreniii, who have poorer health, nutritioniv and cognitive developmentv. Thus the poverty cycle is continued.

The Bangladesh government, like many other developing countries, has made great strides in increasing places in primary schools, however much of this investment will be wasted if the children are unable to benefit fully. The enormous number of malnourished children who almost certainly have poor mental development has implications not only for the individuals but also for national development. There is an urgent need to begin programs to address this problem.

Adoption studies of severely malnourished children have shown that marked improvements in cognitive development are possible if the children are exposed to vastly improved environmentsvi. However malnourished children usually come from extremely poor environments; not only is the housing and sanitation inadequate but the 'microenvironment' is also poor with few toys and little opportunity for playvii. The mothers usually have low levels of education and lack awareness of the importance of play for children's development.

Recently, there has been increasing concern among international agencies and national governments over the loss of human potential in children growing up with poverty and malnutrition and possible ways of improving the situation are being exploredviii,ix,x.

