## Treatment Trial

### Samples

The study will be conducted in BINP nutrition centers in the Narsingdi Thana. Narsingdi which is situated near Dhaka and has a total population of 353,275 out of whom, there are 21,090 children below the age of 2 years. About 2229 of these children require nutritional supplementation and are enrolled in the BINP community nutrition centers. Narsingdi thana comprises 14 unions with 17-29 feeding centers in each union making a total of 326 feeding centers. Only six of these unions are accessible to Dhaka. For ethical reasons randomization into intervention and control will be by centers and not within each center. Twenty feeding centers from the two unions most accessible to Dhaka, will be selected to participate in the study. Only centers expected to enrol at least 10 children in the five month enrolment period will be selected. The sampling will be in two steps. In the first step, centers that are so close to each other that there is a high probability of the mothers or staff mixing socially, will be formed into clusters. One center from each cluster will then be randomly selected for further sampling. The first stage should prevent any spill over between treatment groups. In the second step 10 centers will be randomly selected for the intervention group and 10 for the control group, from the two unions.

A sample of 84 in each group will be sufficient to detect a difference of 6 developmental quotient (DQ) points between the groups with a power of 90% at the 5% level of significance. Assuming a loss of 16% we need 100 children in each group.

The study will have 3 groups making a total of 300 children who will have all measurements. However, because we want to assess the feasibility of incorporating this programme into a service model we will enrol into the intervention all children who present at the centers and fit the enrolment criteria during the enrolment period. The extra children will not have the measurements but enrolling all available children into the intervention will enable us to determine any problem with implementation at a service level.

**Treatment group:** The first 10 children referred to each intervention feeding center after the beginning of the study, and fulfil the selection criteria will be enrolled making a total of 100. However, all the children attending the intervention centers will have play opportunities.

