**Control group:** The first 10 children referred to each control feeding center after the beginning of the study and fulfil the selection criteria will be enrolled making a total of 100.

**Inclusion criteria:** weights for age  $<-2sd$ , aged between 6 and 24 months, mothers agree to participate in the study and intend to stay in the area for the next year.

**Exclusion criteria:** twins and disabled children will be included in the intervention for ethical and demonstration purposes but will not be part of the evaluated sample.

**Comparison group:** The child living nearest to every treated malnourished child with weight for age  $>-1sd$ , of the same age ( $\pm$  one month) and sex, maternal education and standard of housing will be enrolled making a total of 100.

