## Measurements

The Drs [name] and [name] will do the piloting and quality control of all measurements.

**Developmental level:** The infants will be assessed on the Bayley Scales of Mental Development at the beginning and end of the study. We have used these scales before in Bangladesh and good interobserver reliability was attained. The assessments will be done by one of two trained female psychologists who are unaware of the children's group assignment. Care will be taken to keep the testers blind to the child's group and the testing will not be done in the feeding centers.

**Behavior:** The children's behavior during the tests will be rated by the testers on five 9 point scales: the amount of vocalisation, co-operation with the test procedure, activity level, emotional tone and response to examiner. These scales have also been used before in Bangladesh and are modified from those of Bayley and Wolke et alxxi.

**Temperament:** At the end of the study the mothers will be given a questionnaire by the psychologists concerning their child's temperament. There is no standardised test for Bangladeshi children. We will therefore pilot an instrument developed by Mary Rothbartxxii and one being developed by Theodore Wachs from Purdue University for use in Jamaica and Peru and combine and modify the instruments where necessary. The following behaviors will be investigated: activity level, positive emotionality (smiling/laughing), negative emotionality (fussing/crying), social approach (response to strange adults), object fear (fear of new objects), attention/orientation, manageability (response to frustration/ co-operativeness), soothability (reduction of distress in response to soothing). These behaviors are well recognised components of temperamentxxiii.

**Anthropometry:** All children will have their weights, lengths, head and mid upper arm circumferences measured using standard techniques on enrolment and every 3 months by the research assistant.

**Socio-economic background and stimulation in the home:** All homes will be visited at the beginning of the study and information will be sought on the families' wealth, standard of housing, family structure and parental characteristics. The stimulation in the home will be assessed using a modified version of the Betty Caldwell home inventoryxxiv, which was modified for Bangladesh in a previous study by this research group.

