## Data Analysis

Describe plans for data analysis. Indicate whether data will be analyzed by the investigators themselves or by other professionals. Specify what statistical softwares packages will be used and if the study is blinded, when the code will be opened. For clinical trials, indicate if interim data analysis will be required to monitor further progress of the study. (TYPE WITHIN THE PROVIDED SPACE).

The qualitative data will be analysed using the framework procedures identified by Ritchie and Spencerxxv including indexing, charting, mapping and interpretation.

For the quantitative data, all test records will be checked by a second person and double entered into the computer. All continuous variables will be examined for normality and transformed if necessary. Initial differences between the randomized malnourished groups will be examined using t-tests or analysis of variance for normally distributed data and chi-squared or Mann-Whitney for non-normal data. To compare initial differences between the adequately nourished and malnourished groups the enrolment data for the two malnourished groups will first be combined. When analyzing behavioral data, age and sex will be controlled if they are significantly related to the outcome variable.

As the sample is clustered into feeding centers, multi-level modelling will be used to examine the treatment effect on the children's development, behavior, and temperament and on the maternal outcomes. For this analysis, we will use the computer package designed by the Institute of Education, Londonxxvi. The model used will have 3 levels, the individual child, the feeding centers and the treatment group. With this model we will be able to control for random variance at each of these levels and to examine whether treatment has different effects in different centers.

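### The protocol seeks a deficit caused by malnutrition, but its stated baseline comparison names no home or family covariate, so part of a home-environment difference may be counted as malnutrition

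*Protocol*

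**What the plan says.** The Specific Aims name, as an additional aim, finding the deficit in children's "development and behavior attributed to protein energy malnutrition". The contrast is observational: children below -2 SD weight for age against children above -1 SD.

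The Background says that malnourished children usually live in very poor surroundings and that their immediate environment "is also poor with few toys and little opportunity for play". Under the justification of the study, it adds that the home may modify the effects of malnutrition, and that socio-economic background and home stimulation will be studied in relation to those effects. No method is given there.

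The comparison child is the one living nearest to each treated malnourished child and of the same age within a month; the text continues "and sex, maternal education and standard of housing will be enrolled making a total of 100". Study Design describes these children more broadly, as similar to the intervened children in socio-economic background.

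On data collection, Samples states: "The study will have 3 groups making a total of 300 children who will have all measurements". Measurements provides for a visit to every home at the start, covering wealth, housing, family structure and parental characteristics, and adds: "The stimulation in the home will be assessed using a modified version" of a published home inventory.

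Data Analysis says of this contrast: "To compare initial differences between the adequately nourished and malnourished groups the enrolment data for the two malnourished groups will first be combined". The only covariates that section names are age and sex, for behavioral data, and only if they are significantly related to the outcome. The multilevel model is specified for the treatment effect.

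**The concern.** The protocol itself supplies both links of a confounding path. It ties malnutrition to poor stimulation at home. Its account of the Jamaican trial in stunted children says that stimulation and supplementation each improved development independently. A simple difference between malnourished and adequately nourished children can therefore contain a home-environment component as well as a nutritional one, and the aim asks for the nutritional one.

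The Background shows that the investigators saw the issue, yet the analysis section does not use the variables gathered to address it. The likely direction is an overstated deficit. Home stimulation is also the factor the trial intervenes on, so mixing it into the malnutrition deficit would blur any later statement about how much of that deficit the program recovers.

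**Working it through.** **1. The plan's own figures.** Samples gives 84 evaluable children per group for 6 DQ points, 90% power, 5% significance and 16% loss, but no SD.
- Loss: 84 / (1 − 0.16) = 100 per group, as stated.
- Implied SD (two-sided test): 6 / [√(2/84) × (1.960 + 1.282)] ≈ 12.0. An SD of 15 would need 132 per group and an SD of 16 would need 150.

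SD 12 is therefore an inference from the sample size and is used below only as an assumption.

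**2. What controls each factor in the baseline contrast.**

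| Factor | Treated v comparison | Control-center v comparison | Covariate named in Data Analysis |
|---|---|---|---|
| Age, sex | matched | not matched | behavioral data only, if significant |
| Maternal education, housing, residence | matched | not matched | none |
| Wealth, family structure | not matched as such | not matched | none |
| Home stimulation | not matched | not matched | none |

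The pooled malnourished group has 200 children. The 100 from control centers have no matched counterpart.

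**3. Illustrative size.** Let d be the standardized home-score difference left after matching, and b the standardized slope of DQ on home score given the matched factors. Then bias = b × d × SD. Neither b nor d is in the documents. The assumed ranges are d = 0 to 0.6 and b = 0.1 to 0.4, with SD 12:
- d = 0: bias 0, whatever b is
- d = 0.1, b = 0.1: 0.1 × 0.1 × 12 = 0.12 points
- d = 0.4, b = 0.3: 0.3 × 0.4 × 12 = 1.44 points
- d = 0.6, b = 0.4: 0.4 × 0.6 × 12 = 2.88 points, or 48% of the 6-point difference

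**4. Effect on the test if there were no true deficit.** SE = 12 × √(1/200 + 1/100) = 1.47, ignoring matching and clustering. The probability of a two-sided 5% rejection is:

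| Bias (DQ points) | 0 | 0.96 | 1.44 | 1.92 | 2.88 |
|---|---|---|---|---|---|
| Rejection probability | 5% | 10% | 16.5% | 26% | 50% |

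Bias and SE both scale with the SD, so for given b and d these probabilities do not depend on the value of 12. The bias in points does: at SD 15 the top of the range would be 0.4 × 0.6 × 15 = 3.6.

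**The case against.** Four arguments count on the other side.

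- **The protocol is not silent.** The Background commits to relating home and socio-economic data to the effects of malnutrition, and a covariate list for a non-randomized secondary contrast could sit in an analysis plan that is not shown. It is true that Data Analysis nowhere says the comparison will be unadjusted. But that section does state the pooling and a covariate rule, and neither reflects the commitment. The Background's language is mainly about modification of effects, which is a different matter from adjustment.
- **Matching removes part of the problem.** The passage on few toys describes malnourished children in general, alongside poor housing and low maternal education, and both of those are matched. This stands for the treated children. For the control-center children, randomization of centers should give similar family background on average. With 10 centers per arm, however, chance differences remain, and the design does not match them.
- **Adjustment may remove too much.** If a malnourished child receives less stimulation because of the malnutrition, adjusting for home score takes out part of the effect sought. This stands, and it is why the home-adjusted figure should not be the only one reported.
- **The stakes are limited.** This is an additional aim. The randomized comparison is untouched, and asking whether children reach levels normal for their community is descriptive.

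A reader might infer that the whole effect of a poor home is booked as malnutrition, or that an observed deficit could be wholly spurious. The documents do not support this: only what remains after matching is at issue, and its size is unknown and could be zero. A larger assumed gap (d = 0.8, b = 0.4) gives 0.4 × 0.8 × 12 = 3.84 points, but nothing in the protocol points to a gap of that size between matched neighbors.

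**Conclusion.** The point holds in a limited form. The aim is causal, while the stated comparison names no home or family covariate and includes 100 malnourished children outside the matching. The analysis section thus falls short of the Background's own commitment. Differences in home stimulation, wealth and family structure, and for control-center children in the matched factors too, may be partly counted as a malnutrition deficit.

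The size cannot be derived from the documents. The range of 0 to about 3 DQ points rests on an SD of 12 implied by the sample size and on assumed values for the residual home difference and the slope. The matter is worth correcting because the contrast is a declared aim that 100 of the 300 children are enrolled to serve. It does not affect the validity of the randomized trial.

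**What to change.** In Data Analysis, specify for the baseline contrast between malnourished and adequately nourished children:

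1. The unadjusted difference, described as associated with malnutrition and not as attributed to it.
2. A regression estimate with covariates fixed in advance and kept whatever their p-value: the matching factors (age, sex, area, maternal education, housing), wealth, family structure and parental education. Including the matching factors also deals with the control-center children who have no matched counterpart.
3. The same regression with the baseline home inventory score added.

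Report all three side by side. State that the third may be conservative if malnutrition itself lowers stimulation, so that it is not presented as the single correct value.

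The cost is a few lines of text and slightly more analysis; no new data are needed. The reported deficit may turn out smaller than the unadjusted one.

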## OBJECTIVES

1. Using a randomised controlled design, to establish a child development intervention in 10 feeding centers serving moderately and severely malnourished children aged 6-24 months and their mothers.
2. To compare the intervention group with a control group who also suffer from moderate or severe malnutrition and attend 10 other centers on the following: growth in height and weight for height, behavior, temperament and developmental levels of the children, the mothers' child rearing practices and knowledge of child development, health and nutrition.
3. On the above variables to compare the malnourished groups with a group of adequately nourished children matched for area of residence, maternal education and standard of housing.
4. To determine the logistical problems with implementation of the program.
5. At the end of the study to train existing staff from the control feeding centers in the conduct of the program.

## Background of the Project including Preliminary Observations

---

Describe the relevant background of the proposed study. Discuss the previous related works on the subject by citing specific references. Describe logically how the present hypothesis is supported by the relevant background observations including any preliminary results that may be available. Critically analyze available knowledge in the field of the proposed study and discuss the questions and gaps in the knowledge that need to be fulfilled to achieve the proposed goals. Provide scientific validity of the hypothesis on the basis of background information. If there is no sufficient information on the subject, indicate the need to develop new knowledge. Also include the **significance and rationale** of the proposed work by specifically discussing how these accomplishments will bring benefit to human health in relation to biomedical, social, and environmental perspectives. (DO NOT EXCEED 5 PAGES. USE CONTINUATION SHEETS).

---

**Introduction:** This proposal concerns incorporating a low cost, feasible, and culturally appropriate program of child development activities into the Bangladeshi Integrated Nutrition Project (BINP) feeding centers with the aim of improving the social and cognitive development of severely malnourished children and the child rearing skills of their mothers. The study will be based at the International Center for Diarrheal Diseases Research in Bangladesh (ICDDR,B) and is a collaboration between ICDDR,B, the Institute of Nutrition and Food Science, Dhaka University, and the Center for International Child Health, Institute of Child Health, University College London.

In recent years, there has been a marked decline in infant mortality rates in nearly all developing countries. In Bangladesh, rates have fallen from 151 per 1,000 in 1960 to 83 in 1996. Although increasing numbers of children are surviving, the quality of many children's lives remains extremely poor. An enormous number of children under five years are malnourished, as many as 56% are moderately or severely underweight and 18% are moderately or severely wastedi. Many studies have shown that malnutrition of this degree is highly likely to detrimentally affect children's cognitive, motor and social developmentii. They are likely to fail in school and subsequently have poor employment opportunities. Compared with better-educated parents, poorly educated parents tend to have larger numbers of childreniii, who have poorer health, nutritioniv and cognitive developmentv. Thus the poverty cycle is continued.

The Bangladesh government, like many other developing countries, has made great strides in increasing places in primary schools, however much of this investment will be wasted if the children are unable to benefit fully. The enormous number of malnourished children who almost certainly have poor mental development has implications not only for the individuals but also for national development. There is an urgent need to begin programs to address this problem.

Adoption studies of severely malnourished children have shown that marked improvements in cognitive development are possible if the children are exposed to vastly improved environmentsvi. However malnourished children usually come from extremely poor environments; not only is the housing and sanitation inadequate but the 'microenvironment' is also poor with few toys and little opportunity for playvii. The mothers usually have low levels of education and lack awareness of the importance of play for children's development.

Recently, there has been increasing concern among international agencies and national governments over the loss of human potential in children growing up with poverty and malnutrition and possible ways of improving the situation are being exploredviii,ix,x.

**Interventions in developed countries:** Research into early childhood education programs in the USA shows that deprived children generally improve in cognitive development while the programs are running and many show sustained benefits in school performance and social development. However the more successful programs have tended to be center based, intensive and high cost, and the children have not usually been undernourished. Therefore the model is probably not useful for developing countries. The challenge is to find low cost and culturally appropriate ways of improving these children's development.

**Intervention studies in developing countries:** Although interventions have been run with deprived children in several developing countries, extremely few have been rigorously evaluatedx. Two early interventions with severely malnourished children used highly trained staff but restricted the duration to the time the children spent in hospitalxii or rehabilitation centerxiii. The children showed immediate cognitive benefits but the gains were transient and no longer present 12 months later. In Jamaica, investigators took a different approach, in which paraprofessionals (aides), with relatively little training, visited the homes over a much longer period. The aides demonstrated play techniques using toys made from discarded materials and focused on the mothers as well as the children. The aims were to improve maternal child interactions, the mothers' knowledge of child development and their teaching techniquesxiv,xv,xvi. The intention was to use the mothers as the intervention agent and it was expected that other children in the family would also benefit. The first study involved severely malnourished children who were in hospital at the beginning of the intervention. They were played with daily in hospital then visited at home for three years following leaving hospital. The children showed marked benefits that were sustained at least up to the age of 16 years. A second study involved moderately growth retarded (stunted) children who were identified in the community and visited for two years. The children were randomly assigned into four groups: supplemented, stimulated, both interventions and control. By the end of the intervention, the children showed independent benefits to their psychomotor development from both stimulation and supplementation, and the group receiving both treatments showed the greatest gains. At 12 years of age, the children still showed benefits to their IQ from stimulation. Interestingly, benefits were more enduring from stimulation than from supplementation. However supplementation is likely to have a greater impact where malnutrition is more severe. Another Jamaican study with deprived but adequately nourished children, showed that weekly contacts produced greater benefits than two weekly or monthly contactsxvii.

Although the Jamaican approach used paraprofessionals and home made play materials, and was thus low cost compared with North American programs, it may still be too expensive to implement on a large scale in low-income countries. The studies involved frequent individual home visits which are relatively costly and a group approach might reach more children for the same expenditures. The Jamaican government is currently piloting a program working with groups of mothers in order to reduce the costs. Groups may have other benefits to the mothers themselves who will be able to share their problems and make new social contacts.

**Treatment of malnourished children in Bangladesh:** The present BINP program is a major governmental effort to improve malnourished children's nutritional status. It comprises a total of 972 community nutrition centers where malnourished children are referred for supplementary feeding. Children with weights for age below -3 z scores or with growth faltering (<600g per 2 months in under one year of age, <300g in 2 months in under two years) are referred and they are given supplementary feeding. They are discharged when they reach >-2 z scores but monitoring is continued until the children

Principal Investigator: Last, first, middle [name]

are 24 months old. This program should reduce mortality and morbidity in children but it is unlikely to also improve their general cognitive, social and emotional development.

**Justification of proposed study:** The BINP nutrition centers present an opportunity to introduce child development activities into the treatment of malnourished children in order to promote their all round development. We propose to design an intervention that can be added to the present treatment of malnourished children. The intervention will be piloted and evaluated in feeding centers in a randomized controlled trial. Only one small, non-randomized study elsewhere has shown that severely malnourished children gain long-term benefits from psychosocial stimulation and there is a need to replicate the finding.

There is also a need to develop models for promoting child development that are innovative, low cost and feasible and in this study we will pilot such a program. It is intended to work with groups of mothers and children in the feeding centers. The program will last for as long as one year because short-term interventions have had only transient benefits. We will also meet with the mothers every week as this frequency has been shown to be most effective.

It is important that the intervention is culturally appropriate. We recently assessed the stimulation in the home in a study in Dhaka and obtained some useful data. However, more qualitative information would be helpful to enable us to design a suitable intervention, which builds onto the strengths of the culture. We will therefore conduct a rapid survey of child rearing practices in the study villages preceding the study.

In the past researchers have tended to focus on the cognitive effects of malnutritionxviii. There is relatively little information on their social behavior and temperament. We will therefore ask new questions about the temperament of malnourished children.

The effects of malnutrition and intervention may be modified by the children's home environment. For example, malnutrition usually causes smaller deficits in children from middle class homes than in poor homesxix, and intervention is more likely to benefit children in the poorer homesxx. The effect of malnutrition in the extremely poor situations found in Bangladesh may therefore be more devastating than that found in better off countries. There is little information on the development of malnourished Bangladeshi children and this study should increase our understanding of their developmental problems and assist in the design of future interventions. In the present study we will measure the socio-economic background of the families and stimulation in the home in detail and determine how they relate to both the effects of malnutrition and treatment.

Finally, the ICDDR, B in collaboration with Dhaka University intends to develop a group of academics with skills to conduct essential research linking child development to health and nutrition and to design interventions. There is now a small group of researchers with the necessary skills to run and evaluate an intervention. The proposed study will offer an opportunity to strengthen this group and allow them to get further experience and acquire new skills.

